14.3 Analysis Sets

Safety analysis set

The Safety Analysis Set will consist of all randomized subjects who receive at least 1 dose of study medication. The Safety Analysis Set will be used primarily for the analysis of safety data. Subjects will be classified based upon the treatment received.

Full analysis set (FAS)

The FAS will include all randomized subjects who receive at least 1 dose of study medication, who underwent an elective BR surgery as specified in the protocol, and who provided at least 1 post-surgery assessment of the primary endpoint (GIR) during the treatment period. The FAS will be used primarily for the analysis of efficacy data. Participants will be analyzed according to the treatment group to which they are randomized.

Per-protocol analysis (PP) set

The PP set is a subset of the FAS who:

- Had a protocol-specified surgery
- Did not take prohibited medications during the treatment period that could affect the primary endpoint
- Had otherwise complied with the protocol without any other major protocol deviation (any exceptions for inclusion/exclusion criteria granted by the Sponsor/medical monitor will not be considered protocol violations)

Details of the evaluability criteria will be determined before study unblinding and specified in the SAP.

PK analysis set: The PK Analysis set will include all subjects who have available PK data for at least 1 dose of TU-100.

14.4 Handling of Missing Data and Outliers

For incomplete date in safety data such as prior and concomitant medication and AEs, the following rules will be applied.

For partial start date:

- If the month and year are provided and day is missing, and the month and year match the month and the year of the first dose date of TU-100, the day of the first dose date of TU-100 will be imputed.
- If the year is provided and the month and day are missing and the year matches the year of the first dose date of TU-100, the month and day of the first dose date of TU-100 will be imputed. Otherwise, January will be used.
- If the start date is completely missing, the start date will not be imputed.
- If the stop date is complete and the imputed start date is after the actual stop date, then the start date will be imputed as the stop date.

For partial stop dates:

- If the month and year of stop are provided, but the day is missing, then the last day of the month will be used.
- If the year of stop is provided, but the month and day are missing, then December 31st of that year will be used.
- If the stop date is completely missing, then the date of last study visit will be used.

For laboratory test results:

- Results of a nonnumeric qualifier (e.g., “< x” – below the lower limit of quantification or “> x” – above the upper limit of quantification) will be displayed in the data listings as shown in the data, but the numerical value of “x” will be used for calculation of summary statistics.

Missing values for other data points will remain as missing unless otherwise specified. Missing values will not be imputed and only observed values will be used in data analyses and presentations unless otherwise stated. Detailed missing handling rules will be discussed in the SAP.

14.5 Efficacy Analyses

For efficacy endpoints, the analysis on FAS will be considered as the primary analysis while the analysis on the PP population will be considered confirmatory.

14.5.1 Statistical Hypotheses and Tests

The null hypothesis for the primary efficacy endpoint is that at least 1 dose regimen of TU-100 is superior to placebo with respect to the improvement in time to GIR during the post-surgery observation period (up to 10 days), which translates into a greater HR (TU-100 versus placebo).

Symbolically, the hypotheses for each dose level of TU-100 compared with placebo can be written as:

$$\begin{aligned} H_0: \text{HR} &= 1.428 \\ H_A: \text{HR} &> 1.428 \end{aligned}$$

All analyses will be performed based on 1-sided tests at the significance level of 0.05 for the primary endpoint. Nominal *P* values will be reported without any adjustment for multiple endpoints in the study.

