9.3 Measures to Minimize Bias: Study Treatment Assignment and Blinding

9.3.1 Method of Study Treatment Assignment

Subjects will be randomized in a 1:1:1 ratio to TU-100 15 g/day, TU-100 7.5 g/day, or placebo on Day 1 before the first dose of study drug. Subject randomization will be stratified based on surgical approach, i.e., whether surgery was open or laparoscopic.

Subjects who sign an ICF will be assigned a subject number sequentially at screening. The first 3 numbers of a subject number indicate the study center and the last 4 digits indicate the order in which the subject presented to be screened (for example, Subject XXX-XXXX).

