14.2 Determination of Sample Size

The study is expected to enroll approximately 402 eligible subjects (with expected loss to follow-up or censorship of primary endpoint) with 1:1:1 randomization ratio over a post-surgery period (up to 10 days). The study is sized to achieve approximately 87% power to detect a hazard ratio (HR; TU-100 versus placebo) of 1.428 for GIR, which translates into an improvement in median time to GIR from 48 hours (2.0 days) for placebo (reference) to 34 hours (1.4 days) for TU-100 at a 0.05 significance level of one-sided log-ranked test for equality of time to GIR survival curve.

Based on historical evidence, it is assumed that a small proportion of subjects will be lost to follow-up or will have events censored due to required analytical methods. To account for this anticipated loss in contribution of events to the primary endpoint, an additional 36 subjects (approximately 10% of 366) will be enrolled to achieve a final sample size of 402 subjects (134 per group).

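### The primary null hypothesis is worded as superiority and set at the design effect (HR = 1.428), so the test as written has 5% power at the planned effect instead of about 87%

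*Combined protocol and SAP*

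**What the plan says.** Section 14.5.1 states the primary hypotheses twice, in words and in symbols.

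- In words: "The null hypothesis for the primary efficacy endpoint is that at least 1 dose regimen of TU-100 is superior to placebo", in terms of time to GI recovery.
- In symbols: after the lead-in "the hypotheses for each dose level of TU-100 compared with placebo can be written as", it gives H0: HR = 1.428 and HA: HR > 1.428. The event is recovery, so an HR above 1 favours TU-100.
- Test level: "All analyses will be performed based on 1-sided tests at the significance level of 0.05 for the primary endpoint".

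Section 14.2 gives the same number a different role. The trial has "approximately 87% power to detect a hazard ratio (HR; TU-100 versus placebo) of 1.428 for GIR", described as a change in "median time to GIR from 48 hours (2.0 days) for placebo (reference) to 34 hours (1.4 days) for TU-100", tested "at a 0.05 significance level of one-sided log-ranked test for equality of time to GIR survival curve".

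Section 14.5.2 plans a Cox model with a one-sided Wald P value and one-sided 95% confidence limits, plus a stratified log-rank test for each dose. It gives no null value. The synopsis repeats the analysis methods but not the hypotheses.

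**The concern.** There are two separate faults in 14.5.1.

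1. The sentence is inverted. It makes superiority the null, so rejecting the null would mean rejecting superiority.
2. The symbols are shifted. The alternative still points towards benefit, but the null sits at the effect the trial was sized to find. No effect (HR = 1) is in neither hypothesis, and a drug that performs exactly as assumed lies on the null boundary.

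The two statements also disagree with each other: superior to placebo is not the same as HR exactly 1.428. Both disagree with 14.2, where a test of equality means a null of HR = 1.

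This is the decision rule for the primary endpoint. As the protocol stands, an observed HR equal to the planned effect is a success under 14.2 and a failure under 14.5.1. Settling which rule applies after unblinding would be a post hoc choice on the primary endpoint.

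**Working it through.** **Inputs**

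- Design HR 1.428, one-sided alpha 0.05, power about 87%, log-rank test of equality (14.2).
- 402 subjects, of whom 36 are an allowance for loss, leaving 366 (14.2). With 1:1:1 allocation (9.3.1) that is 366/3 = 122 per arm and D = 244 per dose-placebo comparison.
- Assumption: all 244 have the event. Section 14.2 gives subjects, not events; this is relaxed below.
- H0: HR = 1.428 (14.5.1).

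**Formula.** With equal allocation, the log HR estimate has standard error 2/√D = 1/√(D/4). For D = 244, √(D/4) = √61 = 7.810. For a null value h0,

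power = Φ( √(D/4) × ln(HR_true/h0) − 1.645 ).

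**Step 1: reproduce the protocol's figure (h0 = 1).**
ln(1.428) = 0.3563, and 0.3563 × 7.810 = 2.783. Power = Φ(2.783 − 1.645) = Φ(1.138) = **87.2%**, against the stated 87%.
Events needed for 87%: 4 × (1.645 + 1.126)² / 0.3563² ≈ 242, or 243 rounded up to a whole event. The 366 subjects supply 244.
With censoring at 240 hours and exponential medians of 48 and 34 hours, recovery by 240 hours averages 98.1%. That gives about 239 events and 86.7% power.
The ratio 48/34 is 1.412, which gives 85.3%; but 48/1.428 = 33.6 hours, so 34 looks like a rounded median.
The sample size therefore rests on a null of HR = 1.

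**Step 2: the hypotheses as printed (h0 = 1.428).**
At a true HR of 1.428, ln(1.428/1.428) = 0, so power = Φ(−1.645) = **5.0%** for any D.

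| True HR | Power, null 1 | Power, null 1.428 |
|---|---|---|
| 1.428 | 87.2% | 5.0% |
| 1.6 | 97.9% | 22.5% |
| 1.8 | 99.8% | 56.5% |
| 2.0 | >99.9% | 83.8% |

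**Step 3: what each rule requires.**

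- Smallest significant observed HR, null 1: exp(1.645/7.810) = **1.23**.
- Smallest significant observed HR, null 1.428: 1.428 × 1.234 = **1.76**. Equivalently, the one-sided lower 95% limit must exceed 1.428.
- True HR for 87% power, null 1.428: 1.428 × exp(2.771/7.810) = **2.04**.
- At an observed HR of 1.428, the z statistic is 2.78 (one-sided P about 0.003) against a null of 1, and 0 (P = 0.50) against a null of 1.428.

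**Step 4: sensitivity to the event count.** If all 134 + 134 = 268 subjects in a comparison had events, power at 1.428 would be 89.8% against a null of 1 and still 5.0% against a null of 1.428. The critical observed HRs would be 1.22 and 1.75.

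**The case against.** The strongest reply is that nobody would run the test in 14.5.1. The analyses actually described, a Cox Wald test and a stratified log-rank test, test HR = 1 in their standard form. Nothing in 14.5.2 mentions an offset, a shifted null or a confidence limit compared with 1.428. Since 14.2 also sizes on equality, the planned analysis probably keeps its 87% power and the 5% is hypothetical. This is right about the likely intent, and it means the sample size is sound. It does not remove the contradiction. Section 14.5.2 names tests but no null value, so the only null in the text is the wrong one.

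Three smaller points are fair:

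- The 5% figure measures the shifted symbols only. The inverted sentence is a separate fault with no power attached to it.
- Section 14.1 says a later SAP prevails where it differs from the protocol. The text reviewed contains no SAP statement of the hypotheses, so whether the SAP corrects or repeats the error is unknown.
- Correcting the per-dose hypotheses does not settle whether a positive result for either dose is enough. The sentence in 14.5.1 refers to at least one dose, and 14.5.4 plans no multiplicity adjustment.

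**Conclusion.** The concern holds. Section 14.5.1 makes the claim to be proven the null in words, and the design alternative the null in symbols; both conflict with 14.2. Followed literally, the symbolic test has 5.0% power at the planned effect, against 87.2% for the test the trial was sized on. The threshold for the observed HR moves from about 1.23 to about 1.76.

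The 5.0% does not depend on the number of events. The thresholds and the 87.2% assume proportional hazards, equal allocation and 244 events per comparison; allowing for censoring at 240 hours lowers the 87.2% only to 86.7%. The loss of power is conditional on 14.5.1 being applied as printed, and the fault is most likely a drafting error. It must still be corrected, because it is the only stated null for the primary endpoint.

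**What to change.** Rewrite 14.5.1 so that, for each TU-100 dose against placebo, it reads H0: HR ≤ 1 versus HA: HR > 1, tested one-sided at 0.05. State in words that the null is no improvement over placebo in time to GI recovery. Keep 1.428 only in 14.2, as the design alternative. Check that the SAP carries the same statement, since it takes precedence. While the paragraph is open, say whether success means either dose or both; that question is separate from this correction.

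The cost is a few lines of text. Sample size and data collection are unaffected, and a standard Cox or log-rank program already tests HR = 1. Because 14.1 requires an amendment when a principal feature changes, the correction should be documented before unblinding.

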14.5.2 Analysis of Primary Efficacy Endpoint

The primary efficacy variable is time to gastrointestinal recovery (TGIR), a composite endpoint defined as the following:

TGIR = maximum (time to first toleration of liquids; time to first BM OR [absence of distention AND bowel sounds AND flatus])

Time to an event is defined as the elapsed time, in hours, from the end of surgery to the time of the first event, to be calculated as:

$$\text{Time to event (hours)} = (\text{time of the event} - \text{time of end of surgery})$$

When TGIR is greater than 10 days (240 hours), it will be censored at 10 days. Censoring rules for other secondary time-event endpoints will be discussed in the SAP.

The primary analysis of TGIR will be based on the Cox proportional hazard model (Cox PH) that includes the main effects for treatment and surgical approach (open versus laparoscopic). The estimates of time to event for the quartiles (25%, 50%, 75%), hazard ratios and their corresponding one-sided 95% confidence intervals (CIs), the Wald Chi-square one-sided *P* values from the Cox analysis will be summarized. The ties in the data will be handled by the Breslow method.

A secondary analysis will be applied for TGIR using the Cox PH model including main effects for treatment, surgical approach (open versus laparoscopic), and covariates such as surgical type, gender, age (years), post-operation opioid consumption (mg morphine equivalents; [APPENDIX 2](#)), thoracic epidural use, and surgery duration (hours). Backward method will be used to select statistically significant covariates (*P* < 0.1). Adjusted *P* value and HR will be provided after the final model is selected.

In addition, TGIR will be assessed for TU-100 versus placebo at each dose level using a stratified log-rank with the one stratum used for randomization: surgical approach (open versus laparoscopic). The Kaplan-Meier estimate of the median TGIR and the corresponding 1-sided 95% CIs calculated using the Greenwood's formula will be presented. Plot of the Kaplan-Meier estimate of the survival distribution function over time will be presented. The restricted mean survival time (RMST) ([Uno 2015](#)) at time t^* using the Kaplan-Meier estimate of the survival function will also be provided, where t^* is the minimum of the largest observed time (event or censored) in each of the 2 groups. Furthermore, the difference in RMST, as well as the ratio of RMST between 2 groups will be evaluated. Similar analyses will be applied for other time to event efficacy endpoints.

The effect of some additional potential covariates on treatment effect may also be evaluated using appropriate methods. Sensitivity analyses for TGIR will be described in the SAP.

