Statistical Methods and Planned Analyses:	
Populations:
 
Safety analysis set: All randomized subjects who receive at least 1 dose of study medication. The Safety Analysis Set will be used primarily for the analysis of safety data. Subjects will be classified based upon the treatment received.
 
Full analysis set (FAS): All randomized subjects who receive at least 1 dose of study medication, who underwent an elective BR surgery as specified in the protocol, and who provided at least 1 post-surgery assessment of the primary endpoint (GIR) during the treatment period. The FAS will be used primarily for the analysis of efficacy data. Participants will be analyzed according to the treatment group to which they are randomized.
 
Per-protocol analysis (PP) set: A subset of the FAS who:
 
 Had a protocol-specified surgery Did not take prohibited medications during the treatment period that could affect the primary endpoint Had otherwise complied with the protocol without any other major protocol deviation (any exceptions for inclusion/exclusion criteria granted by the Sponsor/medical monitor will not be considered protocol violations) 
PK analysis set: All subjects who have PK data available for at least 1 dose of TU-100.
 
The primary efficacy variable is time to TGIR, a composite endpoint defined as the following: $\text{TGIR} = \text{maximum}(\text{time to first toleration of liquids; time to first BM OR [absence of distention AND bowel sounds AND flatus]})$
 
Time to an event is defined as the elapsed time, in hours, from the end of surgery to the time of the first event, to be calculated as:
 $\text{Time to event (hours)} = (\text{time of the event} - \text{time of end of surgery})$ 
The primary analysis of TGIR will be based on the Cox proportional hazard model (Cox PH) that includes the main effects for treatment and surgical approach (open versus laparoscopic). The estimates of time to event for the quartiles (25%, 50%, 75%), hazard ratios and their corresponding one-sided 95% confidence intervals (CIs), the Wald Chi-square one-sided P values from the Cox analysis will be summarized. The ties in the data will be handled by the Breslow method.
 
A secondary analysis will be applied for TGIR using the Cox PH model including main effects for treatment, surgical approach (open versus laparoscopic), and covariates such as surgical type, gender, age (years), post-operation opioid consumption (mg morphine equivalents), thoracic epidural use, and surgery duration (hours). Backward method will be used to select statistically significant covariates ($P < 0.1$). Adjusted P value and hazard ratio (HR) will be provided after the final model is selected.
 
In addition, TGIR will be assessed for TU-100 versus placebo at each dose level using a stratified log-rank with the one stratum used for randomization: surgical approach (open versus laparoscopic). The Kaplan-Meier estimate of the median TGIR and the corresponding 1-sided 95% CIs calculated using the Greenwood's formula will be presented. Plot of the Kaplan-Meier estimate of the survival distribution function over time will be presented. The restricted mean survival time (RMST) at time t^* using the Kaplan-Meier estimate of the survival function will also be provided, where t^* is the minimum of the largest observed time (event or censored) in each of the 2 groups. Furthermore, the difference in RMST, as well as the ratio of RMST between 2 groups will be evaluated. Similar analyses will be applied for other time to event efficacy endpoints.
 
A secondary efficacy variable, time to ready for discharge (based solely on the treating medical team's determination of GI recovery), which is defined as the time to the assessment date of "ready for hospital discharge." Length of stay is based on the time to the calendar day of discharge order written from the calendar day of surgery.
 
Treatment effect on other numeric variables will be analyzed using an analysis of variance (ANOVA) if normally distributed, or the Wilcoxon rank sum test otherwise. Treatment effect on categorical variables will be analyzed using the stratified Miettinen and Nurminen (M&N) method (stratified by surgical approach), or the logistic regression model if appropriate.

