6.2.4 Exploratory Endpoints

Other exploratory endpoints of this study are as follows:

- Subject-reported (electronic diary [eDiary]) occurrence of nausea, vomiting and/or retching, and abdominal bloating per day
- Subject-reported (eDiary) number of episodes of vomiting and/or retching per day
- Subject-reported (eDiary) bothersomeness of nausea and abdominal bloating by day
- Incidence and severity of nausea, vomiting/retching, abdominal bloating based on spontaneous AE reporting from safety database
- Postoperative antiemetic rescue
- Postoperative complications
 - Prolonged POI:
 - Minimal incision BR (laparoscopic or robotically-assisted or hand-assisted): Unresolved POI by postoperative Day 3
 - Laparotomy (open) BR: Unresolved POI by postoperative Day 5
 - Note: POI = primary POI (i.e., POI that is not secondary to surgical complication, such as anastomotic leak, abscess formation, or sepsis etc.)
 - Recurrent POI (that prolongs hospital stay or results in readmission – based on investigator assessment)
 - Surgical site infection
 - Anastomotic leak
 - Early postoperative mechanical small bowel obstruction (EPSBO) (Confirmed by the presence of a transition point between dilated and decompressed bowel demonstrated on abdominal imaging)
- Time to discontinue intravenous (IV) fluids
- Time to transition to oral analgesics
- Hospital readmission (within 7 days and within 30 days of discharge)

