14.5.4 Multiplicity Adjustments

No multiplicity adjustments are planned.

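### The primary Cox model adjusts for surgical approach as a main effect; stratifying by approach would drop an unsupported proportional-hazards assumption at almost no cost

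*Combined protocol and SAP*

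**What the plan says.** Section 14.5.2 bases the primary analysis on a "Cox proportional hazard model (Cox PH) that includes the main effects for treatment and surgical approach (open versus laparoscopic". The synopsis repeats this and adds that "the Wald Chi-square one-sided P values from the Cox analysis will be summarized". Ties are handled by the Breslow method and times beyond 240 hours are censored. Section 14.5.4 reads "No multiplicity adjustments are planned", so each dose is compared with placebo at one-sided 0.05.

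Elsewhere the plan treats surgical approach as a stratum. Randomization is stratified by it (9.3.1), and categorical endpoints use a Miettinen-Nurminen analysis stratified by it (14.5.3). Section 14.5.2 adds a further test of the primary endpoint "using a stratified log-rank with the one stratum used for randomization". The sample size in 14.2 also rests on a log-rank test. Sections 14.5.2 and 14.5.3 carry similar analyses to the other time-to-event endpoints.

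The only statement about how recovery differs by approach is the exploratory definition of prolonged ileus in 6.2.4: "Minimal incision BR (laparoscopic or robotically-assisted or hand-assisted): Unresolved POI by postoperative Day 3" and "Laparotomy (open) BR: Unresolved POI by postoperative Day 5". The documents give no expected share of open surgery, no recovery times by approach, no check of proportionality between approaches and no robust variance. Sensitivity analyses for the primary endpoint are left to the SAP.

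**The concern.** A main effect gives both approaches a common baseline hazard, multiplied by one constant for open surgery. If open recovery starts after a delay, the true ratio is near zero early and rises later. The fitted constant then gives open subjects too much weight in early risk sets and too little in late ones. Although approach is only a nuisance factor, this misfit reaches the treatment coefficient. Its model-based standard error is too small, and its estimate can move away from the within-approach hazard ratio.

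The primary P value and hazard ratio are therefore at stake, and by extension the other time-to-event endpoints. In the scenarios where the assumption clearly fails, the error runs toward false positives and an overstated effect. The stratified log-rank test does not have this weakness, but it is supportive and does not replace the primary P value or HR.

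**Working it through.** **1. The plan's own figure.** Section 14.2 states "The study is sized to achieve approximately 87% power to detect a hazard ratio (HR; TU-100 versus placebo) of 1.428 for GIR", "at a 0.05 significance level of one-sided log-ranked test for equality of time to GIR survival curve". With 366 evaluable subjects there are 122 per arm and 244 per comparison. If all have events, Schoenfeld's formula gives z = ln(1.428) × √244 / 2 − 1.645 = 0.3563 × 7.810 − 1.645 = 1.138, a power of 87.2%. The stated power reproduces and is not in dispute.

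**2. What the Day 3 and Day 5 limits imply.** Two readings fit them equally well. Take Weibull recovery times with shape k.
- *Time scaling*, open times 5/3 as long: the open-to-laparoscopic hazard ratio is (3/5)^k at every time, 0.60 for k = 1, 0.46 for k = 1.5 and 0.36 for k = 2. Hazards are exactly proportional and the main-effect model is correct.
- *Rigid delay of 48 hours*: the ratio is 0 up to 48 hours and then ((t − 48)/t)^(k − 1). For k = 1.5 it is √(24/72) = 0.58 at 72 hours, √(48/96) = 0.71 at 96 hours and √(192/240) = 0.89 at 240 hours. Hazards are not proportional.

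**3. Simulation.** From the documents: 122 or 134 per arm, randomization stratified by approach, censoring at 240 hours, one-sided 0.05, true HR 1 or 1.428. Assumed: the open share, the distribution (exponential, Weibull shape 1.5 or 2, lognormal) and the form of the delay. Most runs set the pooled placebo median to the protocol's 48 hours. The Cox code was checked against a standard package. Monte Carlo standard errors are mostly 0.2 to 0.35 points, for example √(0.05 × 0.95 / 4000) = 0.34 points; they are about 0.4 points for the varying-delay runs (3,000 trials).

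| Open versus laparoscopic | Open share | Type I error, main effect | HR, main effect (true 1.428) |
|---|---|---|---|
| Proportional hazards | not varied | 4.9% | not tabulated |
| Scaling 5/3, Weibull | 5% to 35% | 5.0% to 5.5% | 1.43 to 1.44 |
| Scaling 5/3, lognormal | various | 5.5% to 5.8% | about 1.45 |
| Delay 24 h | various | 5.2% to 6.8% | 1.43 to 1.47 |
| Delay 48 h, rigid | 5% | 5.5% | 1.45 |
| Delay 48 h, rigid | 10% | 5.7% to 6.2% | 1.45 (one run) |
| Delay 48 h, rigid | 20% | 7.0% to 7.5% (exponential 6.2%) | 1.46 to 1.49 |
| Delay 48 h, rigid | 30% | 7.1% to 8.6% | about 1.48 to 1.51 |
| Delay 48 h, rigid | 35% | 8.5% to 9.6% | 1.50 to 1.52 |
| Delay averaging 48 h, varying between subjects | 10%, 20%, 30% | 4.9%, 5.4%, 6.2% | not tabulated |

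The rigid 48-hour rows for 20% and 30% include three-arm joint models with 402 subjects: 7.5% and 8.1%, HR 1.49 and 1.51.

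**4. The stratified Cox model on the same data.** Type I error is 4.7% to 5.8% throughout. The mean HR is about 1.42 to 1.45, in most runs about 1.43. Power is about 87% to 90%, within about 3 points of the main-effect model in the two-arm runs. The largest gap is 91.6% against 87.8% (3.8 points), where a three-arm main-effect model was set against a two-arm stratified one. The main-effect model's apparent advantage comes with its larger type I error.

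**5. Robust variance instead.** With a 48-hour delay it brings the error to about 5% to 7%, only a partial correction.

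**The case against.** A reader might infer that the protocol contradicts proportional hazards, and that any later recovery after open surgery raises the error to about 7%. The documents support neither. The Day 3 and Day 5 limits are cut-offs for labelling a complication; they give no recovery-time distribution. They fit a 5/3 scaling as well as a 48-hour shift, and under Weibull scaling the main-effect model is exactly right.

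The rigid 48-hour delay is also severe: no open-surgery subject recovers within 48 hours of surgery. When the delay averages 48 hours but varies between subjects, the excess over the stratified model is at most about 0.7 points (6.2% against 5.5% at 30% open). Some settings also sit badly with section 14.2. A laparoscopic median of 42 hours, 30% open and a 48-hour shift give a pooled placebo median near 58 hours, not 48. That objection is limited, because runs calibrated to 48 hours still give about 7% at 20% open.

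Finally, this is a Phase 2 trial with nominal P values and two doses each tested at 0.05. In one 30%-open scenario the chance of at least one false positive is 9.1% even with stratification, against 12.0% without. The planned stratified log-rank test, Kaplan-Meier curves and restricted mean analysis could also expose a discrepancy.

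These arguments reduce the size and urgency of the point. They do not supply a reason to keep the assumption: where proportional hazards holds, the two models perform alike (4.9% against 5.0%).

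**Conclusion.** The point holds as a low-cost robustness improvement. The primary test relies on proportional hazards between open and laparoscopic surgery, which the documents neither support nor check, and which stratification makes unnecessary.

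The size is conditional. One-sided type I error ranges from about 5% (proportional hazards, Weibull time scaling or few open cases), through 5.2% to 6.8% (24-hour delay), to about 7% to 8.5% (rigid 48-hour delay with 20% to 30% open) and 9.6% at the extreme (35% open). In the 48-hour cases with at least 20% open, the HR is overstated at about 1.46 to 1.52. No single figure can be attributed to this trial, because the open share and the form of the delay are assumptions. It would also be wrong to infer that the primary analysis is invalid or the trial underpowered. Confidence is high in the mechanism and the remedy, and moderate in the magnitude.

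**What to change.** In section 14.5.2 and the synopsis, define the primary analysis as a Cox model with treatment as the covariate, stratified by surgical approach (a STRATA statement in SAS), and take the one-sided Wald test and hazard ratio from that model. Make the same change for the other time-to-event endpoints covered by 14.5.2 and 14.5.3, and carry it into the SAP.

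The cost is one line of wording. No new data, subjects or sample-size revision are needed. The open-versus-laparoscopic hazard ratio is no longer estimated in the primary model; it can be reported descriptively, with Kaplan-Meier curves by approach.
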